5.2 Treatment Regimen

It is expected that treatment will be administered on an outpatient basis. A cycle will be 28 days and there will be a planned 6 cycles of therapy. Therapy will consist of the following, with each cohort consisting of 15 patients each:

5.2.1 Cycle 1

Cohort Ala:

- (i) Rituximab (or rituximab biosimilar) 375 mg/m²/dose intravenously per institutional standards for four weekly treatments for cycle 1 only, starting on day -6.
- (ii) Utomilumab 100mg intravenously over 1 hour on day 2.
- (iii) Avelumab 3mg/kg (dose level 1) or 10mg/kg (dose level 2) intravenously over 1 hour on day 16.

Cohort Alb and B1:

- (i) Rituximab (or rituximab biosimilar) 375 mg/m²/dose intravenously per institutional standards for four weekly treatments for cycle 1 only, starting on day -6.
- (ii) Utomilumab 100mg intravenously over 1 hour on day 2.
- (iii) Avelumab at the recommended phase 2 dose intravenously over 1 hour on day 16.

Cohort A2a, Dose Level 0:

(i) PF-04518600 0.3mg/kg intravenously over 1 hour on day 1 and day 15.

Cohort A2a, Dose Level 1:

- (i) Rituximab (or rituximab biosimilar) 375 mg/m²/dose intravenously per institutional standards for four weekly treatments for cycle 1 only, starting on day -6.
- (ii) PF-04518600 0.3mg/kg intravenously over 1 hour on day 2 and day 16.

Cohort A2a, Dose Level 2:

- (i) Rituximab (or rituximab biosimilar) 375 mg/m²/dose intravenously per institutional standards for four weekly treatments for cycle 1 only, starting on day -6.
- (ii) Utomilumab 100mg intravenously over 1 hour on day 2.
- (iii) PF-04518600 0.3mg/kg intravenously over 1 hour on day 16.

Cohort A2b and B2:

- (i) Rituximab (or rituximab biosimilar) 375 mg/m²/dose intravenously per institutional standards for four weekly treatments for cycle 1 only, starting on day -6.
- (ii) Utomilumab 100mg intravenously over 1 hour on day 2.
- (iii) PF-04518600 0.3mg/kg intravenously over 1 hour on day 16.

Cohort A3a:

(i) Rituximab (or rituximab biosimilar) 375 mg/m²/dose intravenously per institutional standards for four weekly treatments for cycle 1 only, starting on day -6.

- (ii) PF-04518600 0.3mg/kg intravenously over 1 hour on day 2 and day 15. PF-04518600 will be given first and must have completed administration at least 30 minutes (but a maximum of 28 hours) prior to rituximab (day 15)
- (iii) Avelumab 3mg/kg (dose level 1) or 10mg/kg IV (dose level 2) over 1 hour on day 16.

Cohort A3b:

- (i) Rituximab (or rituximab biosimilar) 375 mg/m²/dose intravenously per institutional standards for four weekly treatments for cycle 1 only, starting on day -6.
- (ii) PF-04518600 0.3mg/kg intravenously over 1 hour on day 2 and day 15. PF-04518600 will be given first and must have completed administration at least 30 minutes (but a maximum of 28 hours) prior to rituximab (day 15)
- (iii) Avelumab at the recommended phase 2 dose intravenously over 1 hour on day 16.

5.2.2 Cycle 2-6

Cohort Ala:

- (i) Utomilumab 100mg intravenously over 1 hour once every 4 weeks x 5 (up to 5 additional doses) on day 1 of each cycle. Utomilumab must have completed administration at least 30 minutes (but a maximum of 28 hours) prior to avelumab.
- (ii) Avelumab 3mg/kg (dose level 1) or 10mg/kg (dose level 2) intravenously over 1 hour once every 2 weeks x 10 (up to 10 additional doses), on day 1 and day 15 of each cycle. On days when avelumab will be given in combination with utomilumab it must be given at least 30 minutes (maximum 24+/-4 hours) following the completion of utomilumab.

Cohort A1b and B1:

- (i) Utomilumab 100mg intravenously over 1 hour once every 4 weeks x 5 (up to 5 additional doses) on day 1 of each cycle. Utomilumab must have completed administration at least 30 minutes (but a maximum of 28 hours) prior to avelumab.
- (ii) Avelumab at the recommended phase 2 dose intravenously over 1 hour once every 2 weeks x 10 (up to 10 additional doses), on day 1 and day 15 of each cycle. On days when avelumab will be given in combination with utomilumab it must be given at least 30 minutes (maximum 24+/-4 hours) following the completion of utomilumab.

Cohort A2a, Dose level 0:

- (i) PF-04518600 0.3mg/kg intravenously over 1 hour on day 1 and day 15.
 - **If there is no response on midtreatment scans following cycle 3, patients may get Rituximab (or rituximab biosimilar) 375mg/m2 intravenously on day 1, 8, 15, and 22 of cycle 4, with PF-04518600 0.3mg/kg intravenously over 1 hour on day 1 and day 15 of this cycle. On days when rituximab will be given in combination with PF-04518600 it must be given at least 30 minutes (maximum 28 hours) following the completion of PF-04518600.

Cohort A2a, Dose level 1:

(i) PF-04518600 0.3mg/kg intravenously over 1 hour on day 1 and day 15.

Cohort A2a, Dose level 2:

- Utomilumab 100mg intravenously over 1 hour once every 4 weeks x 5 (up to 5 additional doses), on day 1 of each cycle. Utomilumab must have completed administration at least 30 minutes (but a maximum of 28 hours) prior to PF-04518600.
- (ii) PF-04518600 0.3mg/kg intravenously over 1 hour once every 2 weeks x 10 (up to 10 additional doses), on day 1 and day 15 of each cycle. On days when PF-04518600 will be given in combination with utomilumab it must be given at least 30 minutes (maximum 28 hours) following the completion of utomilumab.

Cohort A2b and B2:

- (i) Utomilumab 100mg intravenously over 1 hour once every 4 weeks x 5 (up to 5 additional doses), on day 1 of each cycle. Utomilumab must have completed administration at least 30 minutes (but a maximum of 28 hours) prior to PF-04518600.
- (ii) PF-04518600 0.3mg/kg intravenously over 1 hour once every 2 weeks x 10 (up to 10 additional doses), on day 1 and day 15 of each cycle. On days when PF-04518600 will be given in combination with utomilumab it must be given at least 30 minutes (maximum 28 hours) following the completion of utomilumab.

Cohort A3a:

- (i) PF-04518600 0.3mg/kg intravenously over 1 hour once every 2 weeks x 10 (up to 10 additional doses), on day 1 and day 15 of each cycle. PF-04518600 will be given first and must have completed administration at least 30 minutes (but a maximum of 28 hours) prior to avelumab
- (ii) Avelumab 3mg/kg (dose level 1) or 10mg/kg (dose level 2) intravenously over 1 hour once every 2 weeks x 10 (up to 10 additional doses), on day 1 and day 15 of each cycle. Avelumab will be given at least 30 minutes (maximum 28 hours) following the completion of PF-04518600.

Cohort A3b:

- (ii) PF-04518600 0.3mg/kg intravenously over 1 hour once every 2 weeks x 10 (up to 10 additional doses), on day 1 and day 15 of each cycle. PF-04518600 will be given first and must have completed administration at least 30 minutes (but a maximum of 28 hours) prior to avelumab
- (iii) Avelumab at the recommended phase 2 dose intravenously over 1 hour once every 2 weeks x 10 (up to 10 additional doses), on day 1 and day 15 of each cycle. Avelumab will be given at least 30 minutes (maximum 28 hours) following the completion of PF-04518600.

5.3 General Concomitant Medication and Supportive Care Guidelines

Medications or vaccinations specifically prohibited in the exclusion criteria are also not allowed during the active treatment period, except for administration of inactivated vaccines (for example, inactivated influenza vaccine). If there is a clinical indication for one of these or other medications or vaccinations specifically prohibited during the trial, permanent discontinuation from study therapy may be required. The Investigator should consult with the Principal investigator about individual cases. The final decision on any supportive therapy or vaccination rests with the Investigator and/or the patient's primary physician. However, the decision to continue the patient on study therapy or medication/vaccination schedule requires the mutual agreement of the Investigator, the Principal investigator, and the patient. Prior/concomitant treatment considered necessary for the patient's well-being may be given at discretion of the treating physician.

Concomitant medications and treatments, including herbal supplements, will be recorded from 28 days prior to the start of study treatment and up to 90 days after the last dose of study treatment (at Days 30, 60, and 90 post-treatment +3 days). Non-Drug Supportive Interventions should be recorded in the CRF including supportive care drugs (eg, antiemetic treatment and prophylaxis), and the drugs used to treat adverse events or chronic diseases, and non-drug supportive interventions (eg, transfusions).

Medications intended solely for supportive care (ie, antiemetics, analgesics, megestrol acetate for anorexia) are allowed.

5.3.1 Pre-medications

Participants will be premedicated as outlined in Section 8.1.2.8 prior to each dose of avelumab and by institutional standards prior to each dose of rituximab, or as needed for utomilumab and/or PF-04518600. On days when patients are receiving multiple infusions, premedications do not need to be redosed prior to subsequent infusions unless it has been > 4 hours since their previous administration or since administration of medications to treat a hypersensitivity reaction.

5.3.2 Antibiotics

Prophylactic antibiotics or anti-virals are not required on this trial.

5.3.3 Hydration

No pre-hydration or hydration is required with this regimen.

5.3.4 Tumor lysis prevention and management

Participants with bulky disease (>10cm in maximal tumor diameter) and/or circulating disease \geq 25,000 circulating malignant cells/ mm³ will receive allopurinol 300mg orally daily for 14 days starting with the first dose of rituximab. All participants will have a complete metabolic panel, phosphorus, LDH and uric acid checked pre-treatment and at each study visit in cycle 1. For

patients deemed at risk for tumor lysis syndrome (TLS) these labs will also be monitored more closely according to institutional practices. The management of established tumor lysis (see appendix B for definition and grading of tumor lysis) should follow standard institutional practice.

5.3.5 Other supportive treatments

Growth factors, blood product transfusions, and the use of bisphosphonates are permitted at the discretion of the treating physician.

Palliative and supportive care for disease related symptoms may be administered at the investigator's discretion and according to any available American Society of Clinical Oncology (ASCO) guidelines.

Patients should receive appropriate supportive care measures as deemed necessary by the treating Investigator including but not limited to the items outlined below:

- Diarrhea: All patients who experience diarrhea should be advised to drink liberal quantities of clear fluids. If sufficient oral fluid intake is not feasible, fluid and electrolytes should be substituted via IV infusion;
- Nausea/Vomiting: Nausea and vomiting should be treated aggressively, and consideration should be given in subsequent cycles to the administration of prophylactic antiemetic therapy according to standard institutional practice. Patients should be strongly encouraged to maintain liberal oral fluid intake.
- Anti-infectives: Patients with a documented infectious complication should receive oral or IV antibiotics or other anti-infective agents as considered appropriate by the treating Investigator for a given infectious condition, according to standard institutional practice. Prophylactic administration should be considered for the cases outlined in Table 2, Management of Immune Related Adverse Events;
- Anti-inflammatory or narcotic analgesics may be offered as needed.

Patients who need to be on anticoagulant therapy during treatment should be treated with low molecular weight heparin. If low molecular weight heparin cannot be administered, coumadin or other coumadin derivatives or other anticoagulants (including direct Xa inhibitors) may be allowed; however, appropriate monitoring of prothrombin time/international normalized ratio (PT/INR) should be performed.

5.3.6 Other Prohibited Concomitant Medications and Treatments

Patients are prohibited from receiving the following therapies during the treatment phase of this trial:

- Anti-cancer systemic chemotherapy or biological therapy.
- Immunotherapy not specified in this protocol.
- Investigational agents other than avelumab and utomilumab.
- Radiation therapy.

- Immunosuppressive drugs, unless otherwise indicated for the treatment of irAEs and for premedication (see Table 2 and Clarification About Steroid Use below), or for treatment of issues unrelated to study drug after consultation with study chair.
- Medications or vaccinations specifically prohibited in the exclusion criteria are also not allowed during the active treatment period; however, the administration of inactivated vaccines (eg, influenza vaccine) is allowed during the study.
- Herbal remedies or vitamins used as anticancer treatments.
- Herbal remedies with immunostimulating properties (eg, mistle toe extract) or known to potentially interfere with major organ function (eg, hypericin).
- Daily intake over 2 grams acetaminophen/paracetamol.

Clarifications About Steroid Use with Utomilumab, Avelumab and/or PF-04518600: Data have indicated that corticosteroids have an adverse effect on T-cell function and that they inhibit and damage lymphocytes.²³ Furthermore, as with all immunotherapies intended to augment cell mediated immunity, there is a risk that concomitant immunosuppressives such as steroids will counteract the intended benefit of the proposed study treatment. However, studies with anti-CTLA-4 compounds have indicated that short-term use of steroids may be employed without compromising clinical outcomes.²⁴ Therefore, the use of steroids during this trial is restricted as follows:

- Therapeutic use: for the treatment of infusion related reactions, premedication for the prevention of an infusion reaction, and short-term treatment of irAEs, steroids are permitted according to the modalities indicated in Table 2: Management of Immune-Related Adverse Events.
- Physiologic use: steroid replacement for adrenal insufficiency at doses equivalent to ≤10 mg prednisone daily is acceptable.

5.4 Criteria for Taking a Participant Off Protocol Therapy

Duration of therapy will depend on individual response, evidence of disease progression and tolerance. In the absence of treatment delays due to adverse event(s), treatment may continue for 25 weeks or until one of the following criteria applies:

- Disease progression
- Intercurrent illness that prevents further administration of treatment
- Unacceptable adverse event(s)
- Participant demonstrates an inability or unwillingness to comply with the oral medication regimen and/or documentation requirements
- Participant decides to withdraw from the protocol therapy
- General or specific changes in the participant's condition render the participant unacceptable for further treatment in the judgment of the treating investigator

Participants will be removed from the protocol therapy when any of these criteria apply. The reason for removal from protocol therapy, and the date the participant was removed, must be documented in the case report form (CRF). Alternative care options will be discussed with the participant.

When a participant is removed from protocol therapy and/or is off of the study, the relevant Off-Treatment/Off-Study information will be updated in OnCore.

5.5 **Duration of Follow Up**

Patients who complete treatment or come off treatment for reasons other than progressive disease (PD) will have active follow up through 24 months or until death, PD, or next treatment, whichever comes first. After 24 months, PD, or next treatment, patients will enter survival follow up. Participants removed from protocol therapy for unacceptable adverse event(s) will be followed until resolution or stabilization of the adverse event.

5.6 Criteria for Taking a Participant Off Study

Participants will be removed from study when any of the following criteria apply:

- Lost to follow-up
- Withdrawal of consent for data submission
- Death

The reason for taking a participant off study, and the date the participant was removed, must be documented in the case report form (CRF). In addition, the study team will ensure Off Treatment/Off Study information is updated in OnCore in accordance with DF/HCC policy REGIST-101.

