Toxicity will be continuously monitored and recorded using CTCAE 4 criteria, up to 30 days following the last dose of the study treatment or until resolution of toxicity to grade 1 or baseline, whichever occurs last. Response will be assessed 4-6 weeks after the completion of therapy (either after cycle 6 of therapy for patients who complete the planned cycles of therapy, or after their last dose of treatment for patients who discontinue treatment before cycle 6) by PET and CT scans of the neck (if involved at baseline), chest, abdomen, and pelvis, as well as at 6, 12, and 18 months from the end of treatment (+/- 2 weeks) in the absence of disease recurrence or progression (PET may be omitted once patient is in CR). In addition, CT scans of the chest, abdomen, and pelvis +/- neck will be obtained 4 weeks (+/- 1 week) after the completion of cycle 3 while on therapy. If patients experience evidence of progressive disease confirmed by imaging while on treatment, they will be allowed to complete treatment if they meet the definition of an indeterminate response according to LyRIC criteria.²

Expected toxicities and potential risks for all drugs are described in Section 6 (Dosing Delays/Dose Modifications). No investigational or commercial agents or therapies other than those described below may be administered with the intent to treat the participant's malignancy.

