7.2 Adverse Event Reporting

In the event of an unanticipated problem or life-threatening complications treating investigators must immediately notify the Overall PI.

Investigators **must** report to the Overall PI any adverse event (AE) that occurs after the initial dose of study treatment, during treatment, or within 30 days of the last dose of treatment on the local institutional SAE form.

The study period, during which AEs and SAEs must be reported, begins after starting the first dose of study treatment and ends 30 days following the last administration of study treatment or study discontinuation/termination, whichever is earlier. After this period, investigators should only report SAEs that are attributed to study treatment. All AEs and SAEs whether volunteered by the subject, discovered by study personnel during questioning, or detected through physical examination, laboratory test, or other means will be assessed and reported, when appropriate. Abnormal laboratory values will not be reported unless deemed to be clinically significant. Each reported AE or SAE will be described by its duration (i.e., start and end dates), regulatory seriousness criteria if applicable, suspected relationship to study therapy, expectedness, and actions taken.

The table below summarizes the requirements for recording safety events on the CRF and for reporting safety events. These requirements are delineated for 3 types of events: (1) SAEs;

(2) non-serious adverse events (AEs); and (3) exposure to the investigational product under study during pregnancy or breastfeeding, and occupational exposure.

For Multi-Center Trials where a DF/HCC investigator is serving as the Sponsor, each participating institution **must** abide by the reporting requirements set by the DF/HCC. This applies to any medical event equivalent to an unexpected grade 2 or 3 with a possible, probable or definite attribution, unexpected grade 4 toxicities, and grade 5 (death) regardless of study phase or attribution.

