8.2.4 Administration

Rituximab is administered in this study at the dose of 375 mg/m^2 weekly for four treatments starting on Day -6. On days when rituximab is to be given with other intravenous agents, it will be given last, at a minimum of 30 minutes (but up to 28 hours) after the last infusion has completed.

Rituximab should not be administered as an IV push or bolus. Premedication with acetaminophen and an antihistamine should be administered 30 minutes before each IV infusion.

Premedication with acetaminophen and an antihistamine is mandatory. If rituximab is administered more than 4 hours after premedication for avelumab, then the premedication must

be repeated. The line should be flushed, according to local practice, between infusions.

Infusions will follow institutional guidelines.

The infusion should be interrupted or slowed for infusion reactions. Upon improvement of symptoms, continue the infusion at one-half the previous rate. Medical management should be instituted (glucocorticoids, epinephrine, bronchodilators, or oxygen) for infusion reactions as needed. Depending on the severity of the infusion reaction and the required interventions, temporarily or permanently discontinue rituximab.

If the infusion cannot be completed within 1 day, the patient is allowed to receive the remainder of the infusion the following day as long as the dose is administered within 2 consecutive days. This will only be allowed if the reason for dose interruption does not include a Grade \geq 3 toxicity attributed to rituximab. Any patient requiring two dose interruptions, each of which prevent administration of the full rituximab dose within 24 hours will be withdrawn from the study.

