- EKGs: Triplicate 12-lead EKGs will be done in cycle 1 in patients in cohorts A2, A3, and B2 on days when PF-04518600 is administered prior to administration. Triplicate 12-lead EKGs will be done on day 1 and 15 of cycles 2-6 in cohorts A2, A3, and B2 prior to therapy on those days. If the mean QTcF is prolonged (>501msec) immediate correction for reversible causes should be performed. If the QTc reverts to <501msec, and in the judgment of the investigator(s) and principal investigator is determined to be due to cause(s) other than investigational product, treatment may be continued with regular EKG monitoring. If in that timeframe the QTcF intervals rise above 501msec the investigational product will be held until the QTcF has not decreased to 480msec of less after 2 weeks, or if at any time a patient has a QTcF interval >515msec or becomes symptomatic, the patient will be removed from the study. Additional triplicate EKGs should be performed as clinically indicated (ie at the time of any cardiac or neurologic AE)
- Echocardiogram (TTE) or multigated acquisition (MUGA) scan: TTE or MUGA scan should be performed every 3 months while on therapy for patients in cohorts A2, A3, and

B2. All patients with an EF<50%, or a decrease from baseline EF of >10%, must be discussed with the principal investigator prior to treatment.

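### Sections 8.2.4 and 10.2 take patients off the study where 5.4 to 5.6 would keep them in follow-up, and 7.2 can then end AE reporting early, so required response, survival and safety data may be lost

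*Combined protocol and SAP*

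**What the plan says.** **Leaving treatment and leaving the study are separate.** Section 5.4 lists reasons to stop protocol therapy, including unacceptable adverse events. Section 5.5 gives patients who stop for any reason other than progression 24 months of active follow-up (ended sooner by death, progression or next treatment), then survival follow-up. Those who stop for toxicity are also followed until the event resolves or stabilises. Section 5.6 covers leaving the study: "Participants will be removed from study when any of the following criteria apply", followed by loss to follow-up, withdrawal of consent for data submission, and death. Sections 5.4 and 5.6 each require the status and date to be recorded.

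**Two rules elsewhere end study participation on other grounds.** Section 8.2.4, on interrupted infusions: "Any patient requiring two dose interruptions, each of which prevent administration of the full rituximab dose within 24 hours will be withdrawn from the study". Section 10.2, on EKGs: "if at any time a patient has a QTcF interval >515msec or becomes symptomatic, the patient will be removed from the study".

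**The end of AE collection is stated in more than one way.** Section 7.2 says the reporting period "ends 30 days following the last administration of study treatment or study discontinuation/termination, whichever is earlier"; after that only treatment-attributed SAEs are reported. The same section also asks for any AE up to 30 days after the last dose, without that cut-off. Section 5.1 monitors toxicity for 30 days after the last dose or "until resolution of toxicity to grade 1 or baseline, whichever occurs last".

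**The concern.** A site applying 8.2.4 or 10.2 literally would record the patient as off study. It could then reasonably stop the end-of-treatment PET/CT, the PFS and OS follow-up and, through 7.2, routine AE reporting. A site applying 5.5 would continue all of these. The same event could give a complete record at one centre and a truncated one at another.

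CR rate is a primary endpoint, DLT counts decide whether a combination moves to part B, and PFS and OS are secondary endpoints. Cohorts have 15 patients, so each incomplete record matters. The removals relate to tolerance or an undelivered dose, so the missing data cannot be assumed to be unrelated to outcome.

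**Working it through.** **1. The passages side by side**

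| Event | Sections 8.2.4, 10.2, 7.2 read literally | Sections 5.1, 5.4, 5.5, 5.6, 11.1 |
|---|---|---|
| Two rituximab interruptions | Off study | Not a 5.6 ground; follow-up continues after treatment stops |
| QTcF above 515 msec or symptoms | Off study | Not a 5.6 ground; unacceptable AEs end therapy (5.4) |
| Response after early stop | Not required once off study | 4 to 6 weeks after last dose (5.1); at treatment withdrawal if none in previous 6 weeks (11.1) |
| End of AE collection | Earlier of 30 days or study discontinuation | Later of 30 days or resolution (5.1) |

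**2. Timing and reach.** Rituximab is scheduled on days -6, 1, 8 and 15, except in A2a dose level 0. The last dose falls 15 - (-6) = 21 days after the first. An 8.2.4 removal would therefore normally precede the 6-week (42-day) safety evaluation in 5.1, the on-treatment CT (placed between C3D22 and C4D1 in 10.2) and the end-of-treatment scan. Such a patient could have no post-baseline response assessment. Section 11.1.2 censors PFS at the last disease evaluation. The QTcF rule affects cohorts A2, A3 and B2, where EKGs are scheduled.

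**3. The plan's own figures (13.2), by exact binomial with n = 15**

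- Part A CR, P(X >= 3): 0.036 at 5% (stated 4%) and 0.873 at 30% (stated 87%).
- Part B CR, P(X >= 6): 0.061 at 20% (stated 6%) and 0.849 at 50% (stated 85%).
- Part A safety, P(X <= 3): 0.091 at a 40% DLT rate (stated 9%).
- Part B safety, P(X <= 2): 0.062 at 35% (stated 6%).

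All reproduce to rounding.

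**4. Sensitivity.** Assume k of 15 patients drop out of the analysis and the count cut-offs stay fixed. Only n changes.

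| k | n | Part A CR: error at 5% / power at 30% | Part B CR: error at 20% / power at 50% | Part A safety pass at 40% | Part B safety pass at 35% |
|---|---|---|---|---|---|
| 0 | 15 | 0.036 / 0.873 | 0.061 / 0.849 | 0.091 | 0.062 |
| 1 | 14 | 0.030 / 0.839 | 0.044 / 0.788 | 0.124 | 0.084 |
| 2 | 13 | 0.025 / 0.798 | 0.030 / 0.709 | 0.169 | 0.113 |
| 3 | 12 | 0.020 / 0.747 | 0.019 / 0.613 | 0.225 | 0.151 |

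For efficacy, both power and type I error fall. For safety, the chance of passing a regimen with an unacceptable rate rises, but only if these patients also leave the DLT count. If they stay in both denominators, n remains 15 and nothing changes through n.

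**5. How often.** The documents give no rate. With an assumed removal probability q per patient, P(at least one of 15) = 1 - (1 - q)^15, which is 0.26, 0.54 and 0.79 for q = 2%, 5% and 10%.

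**The case against.** The strongest reply is that the protocol still asks for the data. Sections 5.1, 5.5 and 11.1 require response assessment and follow-up after treatment stops; 7.2 has its own 30-day sentence and keeps attributed SAEs reportable; 7.4.5 has a separate 30-day SAE period. This stands against any claim that data *do* stop. It does not remove the conflict, because nothing says which instruction prevails.

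Section 5.6 does not say its list is exhaustive, and 4.1 adds another ground (registered but never treated). That is fair, but the conflict with 5.5 does not depend on exhaustiveness. The cut-off in 7.2 could also mean closure of the whole trial rather than one patient's exit. Even so, an earlier-of rule disagrees with the later-of rule in 5.1.

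A reader might infer more than the documents support:

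- *That these are the patients doing worst.* The triggers are an undelivered dose and a QTcF value or symptoms, not disease outcome. The 8.2.4 rule names no grade and is a toxicity rule only by its context.
- *That the CR rate is inflated and success made easier.* Section 13.3 analyses evaluable patients, and the available text does not define the term, so exclusion is an assumption. The success rules are counts (at least 3 or at least 6 CRs); a smaller denominator does not make them easier to meet.
- *That the triggering toxicity goes unrecorded.* It precedes removal and can still be recorded as an AE or DLT. Later events are what is at risk.

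**Conclusion.** The contradiction is real and can be read directly from the text. Sections 8.2.4 and 10.2 end study participation on grounds that 5.6 does not list and that 5.4 and 5.5 handle differently. The AE cut-off in 7.2 conflicts with 5.1 and with 7.2's own 30-day sentence. Followed literally, these rules may cost the end-of-treatment response, PFS, OS and later AEs for the patients concerned.

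The number affected is unknown. The 26% to 79% range rests on assumed rates of 2% to 10%. The power and safety figures assume that removed patients are excluded, which the available text neither states nor rules out. No direction of bias in the CR rate is established. It is a wording conflict, and worth correcting because data not collected at the time may not be recoverable.

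**What to change.** 1. Reconcile 8.2.4 and 10.2 with 5.4 to 5.6 on what each rule ends. The sponsor must settle this. Neither the triggers nor which drugs stop is proposed here; 6.4 and 6.5 allow drug-specific delays, so any substitute wording needs the same care.
2. State in 5.5 or 5.6 that response, PFS, OS and AE follow-up continue under 5.5 after treatment stops, unless a 5.6 criterion applies.
3. In 7.2, delete the cut-off at study discontinuation or termination, so that AE collection matches the later-of rule in 5.1.
4. In 13.3, keep these patients in the CR and DLT denominators, counting a patient with no documented CR as a non-responder. This is conservative for CR, and the continued scans limit how often it is needed.

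The cost is a few wording edits. The visits and scans are already scheduled for other patients who stop early.
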